C.3.12 Aims 1 and 2 potential pitfalls. It is possible that our hepatotoxicity and treatment discontinuation estimates will be lower than in settings where baseline ALT/AST screening is not performed because we will exclude those with baseline elevations (>2x ULN). Based on our prior work (see C.2), we expect only a small proportion will be screened out. However, using the number screened out, we will be able to calculate "worst case scenario" hepatotoxicity rates assuming that these HIV-infected drinkers would have developed Grade 3/4 toxicities while on treatment. It is also possible that adherence rates in the study will be artificially high, due to the frequent adherence and toxicity monitoring. In that case, our estimates of adherence will represent the upper bound, while the comparison of adherence between the two randomization arms will remain important. If

we establish safety without frequent monitoring, then future studies could measure adherence under more real-world conditions.

C.4 Study methods for Aim 3.

Aim 3: To determine whether the benefits of providing TB preventive therapy to HIV-infected drinkers in resource limited settings outweigh the risks compared to no treatment. We hypothesize that providing TB preventive therapy will result in longer life expectancy and quality-adjusted life expectancy than not providing TB preventive therapy (current standard of care).

C.4.1 Overview. We will utilize our previously developed Markov model that simulates TB preventive therapy and the lifetime clinical progression of a cohort of hypothetical individuals.³³ We will modify this model to fit the Ugandan context by including a detailed simulation of TB preventive therapy safety monitoring. We will then leverage the unique toxicity, tolerability, and adherence data collected in Aims 1 and 2, as well as the medical literature, to project long-term outcomes, stratified by level of alcohol consumption, assuming a variety of monitoring approaches. If our hypothesis is correct, this study will provide evidence needed to change the paradigm of TB preventive therapy and extend life-saving treatment to a population at very high risk of death from HIV/TB co-infection. Below we describe the proposed approach.

C.4.2 Model components. The following model components are part of our previously developed model and will be modified for the context of HIV-infected drinkers in Uganda as described.

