Hepatotoxicity. We will substantially enhance our previous model to include detailed simulation of preventive therapy as follows: First, in every treatment month, simulated individuals on therapy will have a probability of developing an ALT or AST elevation and a probability of developing symptoms of hepatotoxicity. Simulated patients will fall into one of 6 toxicity-related health states (3 levels of ALT/AST levels; normal, 3-5x the ULN, >5x ULN) and 2 levels of symptoms (yes/no). The rates of movement between each of the 6 hepatotoxicity states will be a function of the treatment regimen, and an individual's level of alcohol consumption. Each toxicity-related state will be associated with toxicity-related quality of life, and mortality.

Importantly, the model will distinguish between the underlying true ALT/AST value and the clinical awareness of that value. For example, in the simulation model of no monitoring, patients without symptoms whose true ALT/AST is >5x ULN will not be identified, nor their treatment stopped, and they will have an increased risk of developing symptoms and death.

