TB preventive therapy. The ADEPTT study includes frequent assessment of ALT/AST and symptoms. These data, stratified by level of self-reported alcohol consumption, will inform all of the parameters governing movement between toxicity-related health states. Because the study will stop treatment at the identification of any Grade 3/4 hepatotoxicity, we anticipate no medication-related deaths in ADEPTT. Therefore, we will use the medical literature to inform mortality from each toxicity-related health state in the model, as well as the health state utility of patients with toxicity-related symptoms.¹³⁷⁻¹⁴⁰

Progression to active TB and death. Because the number of observable cases of active TB in the cohort after therapy is expected to be low, we will use the medical literature to inform the incidence of active TB, stratified by TST status, without preventive therapy,¹⁴¹⁻¹⁴³ and will account for the reported efficacy of TB preventive therapy.¹⁴⁴⁻¹⁴⁷ We will use reports of health state utility with active TB collected in SSA.¹⁴⁰

Competing risks of death. We will estimate mortality from all causes other than TB using long-term follow-up of cohorts of HIV-infected persons in SSA. We will use the literature to estimate non-TB mortality among a cohort of HIV-infected persons on ART in SSA with baseline CD4>500¹⁴⁹⁻¹⁵² and published reports of the HR for mortality by lower CD4 counts.¹⁵¹⁻¹⁵⁴ We will also use the medical literature to estimate health state utilities for HIV-infected individuals with and without TB.

C.4.4 Aim 3 analyses. We will use the model to simulate the long-term outcomes of a cohort of HIV-infected drinkers in Uganda with demographic and clinical characteristic similar to those of the ADEPT-TB cohort assuming that TB preventive therapy is provided to all HIV-infected patients who drink alcohol using each of the following TB preventive therapy and monitoring strategies:

- (1) No therapy (standard of care)
- (2) TB preventive therapy without hepatotoxicity monitoring unless patient is symptomatic (no monitoring)
- (3) TB preventive therapy with hepatotoxicity monitoring at week 2 of therapy only (week 2 monitoring)
- (4) TB preventive therapy with hepatotoxicity monitoring monthly throughout (monthly monitoring)

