The simulated model outcomes will include: hepatotoxicity events and deaths, counts of treatment completion and non-adherence, cases of active TB, TB deaths, life expectancy, and quality-adjusted life expectancy. We will first compare life expectancy and quality-adjusted life expectancy for “no monitoring” to “no therapy” to determine whether TB preventive therapy provides net benefit to HIV-infected drinkers even when monitoring is simply not possible. Next, we will compare outcomes from “no monitoring,” “week 2 monitoring” and “monthly monitoring”, to identify the optimal monitoring approach in settings that have some ability to monitor liver functions tests. We will define the “optimal” approach as that which maximizes quality-adjusted life expectancy. Once we have modeled outcomes for the simulated cohort, we will investigate whether the approach to TB preventive therapy should differ based on level of drinking alcohol. We may find, for example, that no monitoring is needed for non-heavy drinkers, while it is necessary for heavy and very heavy drinkers.

C.4.5 Sensitivity analyses. We will use one- and two-way deterministic sensitivity analyses to test the role of uncertainty in driving conclusions and to identify model parameters that have the largest impact on outcomes. We will display the results of such deterministic sensitivity analyses in standard format, such as tornado diagrams and two-way sensitivity graphs.¹⁶⁰⁻¹⁶² Next, we will use probabilistic sensitivity analysis (PSA) to quantify the impact of simultaneous uncertainty in all model parameters on the qualitative conclusions of the analysis.^{160,163} PSA defines every model parameter as a probability density function centered around the best estimate of that parameter’s true value. PSA then performs thousands (typically 10,000) of iterations of the simulation, each time drawing a value for each model parameter from its defined probability density function. The end result is N (10,000) realizations of the simulation, each with its own life expectancy and quality-adjusted life expectancy. By comparing the percentage of the simulations whose conclusions concurred with the base case scenario, it is possible to quantify the degree of certainty in the conclusions of the analysis. Model parameters that will be inherently uncertain and candidates for PSA include the efficacy of TB preventive therapy, the rate of reactivation of TB, and the impact of less than perfect adherence.

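### Aim 3 applies toxicity transitions from drinkers who passed a baseline ALT/AST screen to all drinkers where monitoring is not possible, and does not carry the plan's own worst-case rate into the model

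*Combined protocol and SAP*

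**What the plan says.** The eligibility criteria (C.3.3, and the Study Design Overview) exclude anyone with a liver enzyme elevation above 2x ULN at screening. Everyone who contributes on-treatment data has therefore passed that test.

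On model inputs, C.4.3 says that the ADEPTT data, stratified by self-reported drinking, "will inform all of the parameters governing movement between toxicity-related health states". Toxicity-related mortality comes from the literature (C.4.3, Table 4), and so does the probability of symptoms (Table 4).

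C.4.4 gives the simulated cohort "demographic and clinical characteristic similar to those of the ADEPT-TB cohort". On the question of who is treated, the section proceeds by "assuming that TB preventive therapy is provided to all HIV-infected patients who drink alcohol". It compares four strategies: no therapy, therapy with testing only if symptoms occur, therapy with one test at week 2, and therapy with monthly tests. The first comparison, no monitoring against no therapy, is meant "to determine whether TB preventive therapy provides net benefit to HIV-infected drinkers even when monitoring is simply not possible".

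C.4.2 defines the liver enzyme states as "3 levels of ALT/AST levels; normal, 3-5x the ULN, >5x ULN", each with or without symptoms.

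C.3.12, on pitfalls for Aims 1 and 2, says: "It is possible that our hepatotoxicity and treatment discontinuation estimates will be lower than in settings where baseline ALT/AST screening is not performed". It expects few people to be screened out. It also plans a worst-case rate that counts every screened-out drinker as a Grade 3/4 event.

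**The concern.** The people who supply the toxicity transitions are not the people the conclusion is about. A programme that treats every HIV-infected drinker without a baseline liver test would also treat some with enzymes above 2x ULN, and ADEPTT has no on-treatment data from anyone who started there. The plan acknowledges the likely direction of the difference, but in the Aims 1 and 2 section. The inference to settings without liver tests is made in Aim 3, where the point does not reappear in the data sources, strategies, sensitivity analyses or pitfalls.

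The Aim 3 result is intended to support guidance, and C.4.4 foresees a finding that some drinkers need no monitoring. If the toxicity input is too low for the target population, therapy without monitoring is favoured and the value of testing is understated.

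**Working it through.** **The plan's own figure.** C.3.9 expects about 5 events in 180 evaluable drinkers. The exact binomial (Clopper-Pearson) interval for 5/180 = 2.8% is 0.91% to 6.36%, length 5.46%. This reproduces the stated 0.9% to 6.4% and 5.5%.

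**Inputs for an unscreened population.**
- p, Grade 3/4 rate among those screened in: 2.6% (C.3.9 planning value).
- s, share screened out: 7.6% (C.2: elevations of 2-5x ULN among 169 participants tested).
- r, Grade 3/4 rate the screened-out group would have on therapy: not in the documents, so varied. The upper end, 100%, is the C.3.12 worst case.

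**Formula.** Unscreened rate = (1 - s) x p + s x r = 0.924 x 0.026 + 0.076 x r = 0.0240 + 0.076 x r.

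| r | Basis | Unscreened rate | Ratio to 2.6% |
|---|---|---|---|
| 2.6% | equal risk (assumption) | 2.6% | 1.0 |
| 5.2% | relative risk 2 (assumption) | 2.8% | 1.1 |
| 10% | assumption; relative risk 10/2.6 = 3.8 | 3.2% | 1.2 |
| 20% | assumption; relative risk 20/2.6 = 7.7 | 3.9% | 1.5 |
| 100% | C.3.12 worst case | 10.0% | 3.8 |

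If the screened-out share were instead 2%, 5% or 10% (assumptions), the worst case would be 4.5%, 7.5% or 12.3%.

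**Would the planned sensitivity analysis pick this up?** C.4.5 centres each parameter's distribution on its best estimate. With ADEPTT as that estimate, the probabilistic analysis widens the spread but does not move the centre. The expected exact interval stops at 6.4%, below the 10.0% worst case.

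**Crude check on deaths, per 100 treated.**
- Toxicity deaths at the Table 4 maximum of 0.05 per event: 2.6 x 0.05 = 0.13 at the screened-in rate, and 10.0 x 0.05 = 0.50 in the worst case.
- TB deaths averted over five years, using Table 4 incidence (3.41 per 100 person-years, TST positive) and case fatality (0.23): 100 x 0.23 x [exp(-0.1705 x (1 - e)) - exp(-0.1705)], where 0.1705 = 0.0341 x 5 and e is the reduction in TB.
- With e = 30% to 50% (C.4.2), this is 1.0 to 1.7. Removing 9.4% with subclinical TB, who do not benefit, gives 0.9 to 1.6. The Table 4 hazard ratios (0.41 to 0.11) are more favourable, at 2.1 to 3.2 before that removal.
- Even the worst case (0.50) stays below the lowest benefit (0.9). At a 10.0% event rate, break-even needs about 9 deaths per 100 events (0.92/10.0), against a Table 4 maximum of 5.

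**The case against.** The best defence is that the plan already bounds and discloses the issue. The simulated cohort is described as resembling the trial cohort. C.3.12 gives the likely direction of the difference and a worst-case rate. C.4.5 promises one- and two-way deterministic analyses, and its list of probabilistic candidates is not exhaustive. The elevations in C.2 were few, none was Grade 3, and they did not differ by drinking status (p = 0.90). Participants who reach 3-5x ULN without symptoms do not meet the Grade 3/4 definition and may stay on therapy, so some transitions from raised states will be observed.

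Much of this is right, and it rules out several stronger readings.
- A reader might infer that the model omits the highest-risk drinkers and that therapy therefore certainly looks safer than it is. No section gives isoniazid toxicity for people who start at 2-5x ULN, and the plan calls the bias only possible.
- A reader might infer that a setting without monitoring has no baseline test. The strategies are defined by on-treatment testing. C.4.6 names reagent stock-outs as a likely constraint, which does not settle whether a single baseline test could be done. The plan is silent.
- A reader might infer that only the no-monitoring and week-2 strategies are affected. The same transitions feed monthly monitoring too.
- A reader might infer that the net-benefit result would reverse. The death count above does not show that.

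What the defence does not answer is that the cohort description and the provision to all drinkers pull in different directions, and nothing in C.4.3 to C.4.6 resolves them. A deterministic analysis could test the point, but no range or scenario commits it to do so.

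**Conclusion.** The mismatch is in the text and worth correcting before Aim 3 is run. As written, the plan uses a toxicity input that is probably too low for drinkers treated without a baseline liver test, does not say whether such a test is assumed, and leaves its own worst case out of the model.

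On the planning figures, the unscreened Grade 3/4 rate is 1.0 to 3.8 times the 2.6% input. The top of that range requires every screened-out person to have an event, so it is a bound and not a forecast. The size rests on 7.6% being the share screened out, although that figure comes from HIV-infected cohort participants generally rather than drinkers on ART. It also rests on 2.6% applying to screened-in people, although C.3.9 takes it from published studies whose screening cannot be seen here.

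The crude death count leaves therapy ahead of no therapy within Table 4's mortality range. It does not address quality-adjusted life expectancy, the choice between monitoring strategies, differences by drinking level, or mortality above 0.05 in people with prior elevations. Those results could change; how far has not been calculated.

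**What to change.** In C.4.4, state for each strategy whether a baseline ALT/AST test is assumed.

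In C.4.5, add a named sensitivity and threshold analysis:
- Use one common unscreened starting cohort for all four strategies, including no therapy, built from the screening ALT/AST results of all screened drinkers. Changing the cohort for some strategies only would confound the comparisons, and existing elevations are also present without therapy.
- Add a model state for 2-3x ULN, which the current states lack, or state how such people are mapped.
- Vary the screened-out group's toxicity rate from the screened-in rate up to the C.3.12 worst case, and report where net benefit or the optimal strategy changes.

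If this is not done, limit the Aim 3 conclusions to drinkers with baseline ALT/AST no higher than 2x ULN.

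The cost is a little more modelling. The screening results are already collected (C.3.4, Table 3). The result may be less favourable and less precise; if net benefit holds across the range, the conclusion for settings without liver tests is stronger.
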